6.2.1. Preparation and Dispensing

See the IP manual for instructions on how to prepare the study intervention for administration. Study intervention should be prepared and dispensed by an appropriately qualified and experienced member of the study staff (eg, physician, nurse, physician's assistant, nurse practitioner, pharmacy assistant/technician, or pharmacist) as allowed by local, state, and institutional guidance. A second staff member will verify the dispensing.

Study intervention and placebo will be prepared by qualified unblinded site personnel according to the IP manual. The study intervention will be administered in a blinded fashion to the participants.

6.3. Measures to Minimize Bias: Randomization and Blinding

6.3.1. Allocation to Study Intervention

The investigator will assign participant numbers sequentially to the participants as they are screened for the study. Pfizer will provide a randomization schedule to the investigator and, in accordance with the randomization numbers, the participant will receive the study treatment regimen assigned to the corresponding randomization number. It will also appear on the study medication containers. Study intervention will be dispensed at the study visits summarized in the [SoA](#).

Healthy participants will be randomized (once) into the SAD period, at which time, they will receive treatment assignment (PF-07242813 or placebo) for both the SAD and MAD periods. Participants will receive the same blinded treatment assignment (ie, the same dose level of PF-07242813 or placebo) throughout, in both the SAD and MAD cohorts.

- The randomization ratio for the cohorts in the healthy participant SAD/MAD segment will be 3:1 (PF-07242813:Placebo) with the exception of Cohorts 1-3, which will be randomized 1:1.
- The overall randomization ratio for the atopic dermatitis cohorts will be 2:1 (PF-07242813:Placebo) for Cohort 9.

Investigators, all participants and all study personnel involved in the study, with the exception of the pharmacist who prepares the study treatment and, as needed, an individual designated to administer study intervention who has no other involvement with study conduct, personnel, or participants, will remain blinded to each participant's assigned study intervention throughout the course of the study. In order to maintain this blind, an otherwise uninvolved third party will be responsible for the preparation and dispensing of all study intervention and will endeavor to ensure that there are no differences in time taken to dispense or visual presentation following randomization.

In the event of a Quality Assurance audit, the auditor(s) will be allowed access to unblinded study intervention records at the site to verify that randomization/dispensing has been done accurately.

6.3.2. Breaking the Blind

The method for breaking the blind in this study will be manual. A sealed envelope that contains the study intervention assignment(s) for each participant will be provided to the investigator. The sealed envelope will be retained by the investigator (or representative) in a secured area. In case of an emergency, the investigator has the sole responsibility for determining if unblinding of a participant's treatment assignment is warranted. Participant safety must always be the first consideration in making such a determination. If the investigator decides that unblinding is warranted, the investigator should make every effort to contact the sponsor prior to unblinding a participant's treatment assignment unless this could delay further management of the participant. If a participant's treatment assignment is unblinded, the sponsor must be notified within 24 hours after breaking the blind. When the blinding code is broken, the reason must be fully documented and entered on the CRF/DCT.

Once the study is complete, all envelopes (sealed and opened) must be inventoried and retained until authorization for destruction has been provided.

6.4. Study Intervention Compliance

When participants are dosed at the site, they will receive study intervention directly from the investigator or designee, under medical supervision. The date and time of each dose administered in the clinic will be recorded in the source documents and recorded in the CRF. The dose of study intervention and study participant identification will be confirmed at the time of dosing by a member of the study site staff other than the person administering the study intervention.

The site will complete the required dosage Preparation Record located in the IP manual. The use of the Preparation Record is preferred, but it does not preclude the use of an existing appropriate clinical site documentation system. The existing clinical site's documentation system should capture all pertinent/required information on the preparation and administration of the dose. This may be used in place of the Preparation Record after approval from the sponsor and/or designee.

6.5. Concomitant Therapy

All concomitant treatments taken during the study must be recorded with indication, daily dose, and start and stop dates of administration. All participants will be questioned about concomitant treatment at each clinic visit.

Treatments taken within 28 days before the first dose of study investigational product will be documented as a prior treatment. Treatments taken after the first dose of study investigational product will be documented as concomitant treatments.

6.5.1. Concomitant Treatments in Part 1

Use of prescription or nonprescription drugs and dietary and herbal supplements are prohibited within 7 days or 5 half-lives (whichever is longer) prior to the first dose of study intervention. Limited use of nonprescription medications that are not believed to affect participant safety or the overall results of the study may be permitted on a case-by-case basis following approval by the sponsor. Acetaminophen/paracetamol may be used at doses of ≤ 2.5 g/day.

Females taking hormone replacement therapy may be eligible to participate in this study if they are willing to discontinue therapy at least 28 days prior to the first dose of study treatment and remain off hormonal therapy for the duration of the study.

6.5.2. Concomitant Treatments in Part 2

6.5.2.1. Permitted During Study

Participants will be queried about concomitant medication (including topical medications and treatments, over-the-counter and prescription medications and treatments, and vaccinations) at each study visit. All concomitant treatments taken during the study must be recorded with indication, daily dose, and start and stop dates of administration. Any new concomitant medications or dose changes to current concomitant medications should be evaluated for potential new or worsening adverse events.

Treatments taken within 28 days before the first dose of study investigational product will be documented as a prior treatment. Treatments taken after the first dose of study investigational product will be documented as concomitant treatments.

The following concomitant therapies are permitted during the study:

- Oral antihistamines (excluding H4 antagonists) for allergies.
- Stable dose of leukotriene antagonists/modifiers.
- Corticosteroid inhalers at allowed doses (exclusive of high doses of inhaled corticosteroids) is permitted for stable asthma.
- Non-medicated emollient and sunscreen are the only topical products permitted to be used on atopic dermatitis skin during the study. Participants are recommended not to switch the emollient or sunscreen during the study.

A participant who is receiving a permitted concomitant medication for any reason must be on a locally-approved medication and dose for the treated indication, and this must be documented in the CRF. Participants are not allowed any other investigational drugs or treatments during the study.

Participants should refrain from starting new or changing doses of permitted prescription or non-prescription drugs, vitamins, and dietary supplements within 7 days or 5 half-lives (whichever is longer) prior to Day 1 and throughout the study, unless otherwise noted below.

Acetaminophen may be used intermittently (not to exceed 2.5 g/day). Vitamin and mineral supplements of standard potency are allowed in amounts not known to be associated with adverse effects (such as hypervitaminosis).

Participants should report any changes to permitted medications during the study to the investigator as soon as they occur. Medication changes must be documented in the participant's record and CRF.

Unless a prohibited medication or treatment, participants may be administered any other medications necessary for the treatment of concomitant medical disorders as deemed necessary by the treating physician. Following Day 1, addition of concomitant medications or any change in the dosage should be limited to those considered medically essential.

6.5.2.2. Prohibited Treatments and Medications During the Study

Participants are required to discontinue and avoid using certain medications and treatments. Participants should be instructed at each visit to contact the study site investigator promptly if there are any intended changes or additions to concomitant medications. Prohibited medications include:

a. Systemic Corticosteroids:

- Participants receiving systemic corticosteroids within 4 weeks prior to first dose of study intervention or scheduled to receive systemic corticosteroids during the study period for another condition.
- Participants receiving doses of depot preparations of parenteral corticosteroids within 6 weeks of the predicted end of release of the corticosteroid from the depot are excluded.
- An inhaled dose of greater than 1000 µg fluticasone, or an equivalent inhaled corticosteroid, per day.

b. Leukotriene antagonists/modifiers:

- Asthmatic participants taking stable doses of leukotriene antagonists/modifiers for at least 28 days prior to first dose of study drug may be included.

c. Prior or current use of anti-IL-33 targeted therapies.

d. Current or anticipated use of protein therapeutics.

- e. Benralizumab within 12 months of first dose of study intervention, or at any time during the study.
- f. Prior use of the following drugs within 6 months of first dose of study intervention, or at any time during the study:
 - Prior or current use of anti-IL-4 and/or IL-13 targeted therapies (eg, lebrikizumab, tralokinumab).
 - Anti-IL-5 targeted therapies (eg, mepolizumab or reslizumab).
 - Any cell-depleting agents including but not limited to rituximab: within 6 months of first dose of study drug or 5 half-lives (if known), or until lymphocyte count returns to normal, whichever is longer.
- g. Prior use of dupilumab within 4 months of first dose of study intervention, or at any time during the study.
- h. Within 12 weeks of first dose of study intervention, or at any time during the study:
 - Other biologics: within 12 weeks of starting study intervention or 5 half-lives (if known), whichever is longer.
- i. Within 4 weeks of first dose of study intervention, or at any time during the study:
 - Use of oral immune suppressants (eg, cyclosporine A [CsA], azathioprine, MTX, Celcept, mycophenolate-mofetil, interferon-gamma (IFN- γ) within 4 weeks of first dose of study drug or within 5 half-lives (if known), whichever is longer.
 - Any Janus Kinase (JAK) inhibitors, including participation in any clinical studies in which a JAK inhibitor was a possible study treatment.
 - Investigational drugs.
 - Live, attenuated or mRNA vaccines.
 - Oral or topical phosphodiesterase (PDE) 3 or PDE4 antagonists (eg, apremilast, crisaborole); oral/topical histamine H4 antagonists: within 28 days or 5 half-lives whichever is longer prior to first dose of study drug.
 - Phototherapy (NB-UVB) or broad band phototherapy.
 - Regular use (more than 2 visits per week) of a tanning booth/parlor. Use of bronzing creams, gels or sprays within the last 2 weeks.

j. Within 1 week of first dose of study intervention, or at any time during the study:

- Topical treatments that could affect atopic dermatitis (eg, corticosteroids, calcineurin inhibitors, tars, antibiotic creams, topical antihistamines).

A protocol deviation is to be completed for any participant that takes a prohibited treatment or medication during the study and the sponsor is to be notified. The participant may be replaced at the discretion of the sponsor if prohibited treatments have been taken prior to Week 6.

All medications and treatments that could affect atopic dermatitis must be discontinued except permitted concomitant therapies (eg, oral antihistamines). Due to the potential to affect atopic dermatitis with ultraviolet light exposure, participants must also avoid prolonged exposure to the sun and avoid the use of tanning booths, sun lamps or other ultraviolet light sources during the study.

For the purposes of this protocol, dietary supplements are defined as vitamins, minerals, purified food substances, and herbs with pharmaceutical properties. Vitamins, minerals and purified food substances are allowed in amounts not known to be associated with adverse effects (such as hypervitaminosis).

Herbals supplements are only allowed on a case by case basis; please contact the Pfizer staff. Herbal medications with presumed anti-inflammatory properties or known beneficial effects for AD, or that are known to have an effect on drug metabolism (eg St. John's Wort) must be discontinued at least 1 week or 5 half-lives (whichever is longer) before the first dose of study intervention.

Participants should refrain from having any vaccinations during the course of study participation.

Hormonal contraceptives that meet the requirements of this study are allowed to be used in Part 2 participants who are WOCBP (see [Appendix 4](#)).

6.5.3. Rescue Medicine

There is no rescue therapy to reverse the AEs observed with PF-07242813; standard medical supportive care must be provided to manage the AEs.

Part 2 only: Participants randomized into the study are allowed to take other treatments for their disease as prescribed by the investigator, provided they are not included among the prohibited concomitant medications (noted in [Section 6.5.2.2](#)) and the concomitant drugs and doses are maintained unchanged throughout the first 16 weeks of the study. Although no specific rescue treatment is recommended, participants randomized into the study may have access to standard of care therapy, that may include prohibited treatments and medications defined in [Section 6.5.2.2](#), if deemed necessary by the investigator to treat their underlying disease. Since there is no information on drug interactions, the general guidance is, if possible, to defer initiation of treatment until after the primary AD assessments are complete

at Week 6, to start with topical before systemic treatments, and to use fewer immunosuppressing treatments before progressing to more immunosuppressing treatments.

6.6. Dose Modification

6.6.1. Dose Escalation and Stopping Rules (Part 1)

Dose escalation stopping rules will be used to determine whether the maximal tolerated dose has been attained. Dose escalation may be stopped if it is determined that the limits of safety and/or tolerability have been reached. This decision will be made after a discussion takes place between the sponsor study team and the investigator. The sponsor study team may not overrule the investigator's decision to stop dose escalation. If dose escalation is stopped because of any of these criteria, additional cohorts may receive the same or lower doses of the study intervention.

The dose escalation will be terminated based on the following criteria:

- If 50% or more of the participants receiving active drug at a given dose level (but not participants receiving placebo) develop similar clinically significant laboratory, ECG, or vital sign abnormalities, in the same organ class, indicating dose-limiting intolerance.
- If two-thirds of participants at a given dose level develop an individual participant stopping AE (see [Section 7.1](#)).
- Dosing will be paused for any SAE that occurs in a participant receiving active treatment until causality is fully assessed by the PI and sponsor. Dosing may resume if the SAE is determined to be not drug-related by the PI and sponsor. If the SAE is determined to be either drug-related or unknown, either dosing will cease or the SAE will be evaluated by the sponsor's protocol review committee (or similar review group), which is independent of the study team and investigators. If the protocol review committee determines that dosing may resume, a plan that mitigates risks to participants with the resumption of dosing will be implemented. Such a plan could include a revision of inclusion/exclusion criteria, repeating or reducing the dose, or adding appropriate safety monitoring.
- It is determined that the limit of safety and/or tolerability has been reached. This decision will be made following discussions between the study team and the investigator.
- Other findings that, at the discretion of the study team and investigator, indicate that dose escalation should be halted.
- If, at any dose level, the average exposure reaches or exceeds the PK stopping limits, C_{max} of 1020 μ g/mL and AUC_{168H} of 106000 μ g.h/mL

- If, based on the observed data, the group mean C_{max} or AUC (based on total serum concentration) of the next planned dose is projected to exceed the escalation limits, that dose will not be explored. Modified doses may be explored if they are not expected to exceed PK stopping criteria.

Progression to the next dose will occur if the last dose was well tolerated and after satisfactory review of the available safety and PK data.

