4.1.1. Part 1: Single and Multiple Ascending Dose in Healthy Participants

Part 1 is within-cohort randomized, participant- and investigator- blind, sponsor-open, and placebo-controlled investigation of the safety, tolerability, PK, and immunogenicity following SAD and MAD of PF-07242813.

Approximately 97 healthy adult participants will be enrolled at a single study site into the proposed cohorts listed below. Participants may only participate in one cohort.

Participants in the single dose cohorts will be randomized sequentially as follows:

- Cohort 1 (n=4): 0.3 mg active (n=2) or placebo (n=2), IV;
- Cohort 2 (n=4): 1 mg active (n=2) or placebo (n=2), IV;
- Cohort 3 (n=4): 3 mg active (n=2) or placebo (n=2), IV;
- Cohort 4 (n=8): 10 mg active (n=6) or placebo (n=2), IV;
- Cohort 5 (n=8): 30 mg active (n=6) or placebo (n=2), IV;
- Cohort 6 (n=8): 100 mg active (n=6) or placebo (n=2), IV;
- Cohort 7 (n=8): 300 mg active (n=6) or placebo (n=2), IV;
- Cohort 8 (n=8): 1000 mg active (n=6), or placebo (n=2), IV.

Participants in the multiple dose cohorts, will be randomized as follows:

- Cohort 10 (n=8): 15 mg active (n=6) or placebo (n=2), SC x 3 doses Q2W;
- Cohort 11 (n=8): 50 mg active (n=6) or placebo (n=2), SC x 3 doses Q2W;
- Cohort 12 (n=8): 150 mg active (n=6) or placebo (n=2), SC x 3 doses Q2W;
- Cohort 13 (n=8): 300 mg active (n=6) or placebo (n=2), SC x 3 doses Q2W;
- Cohort 14 (n=8, optional): ≤ 1000 mg IV active (n=6) or placebo (n=2), SC x 3 doses Q2W.

The Japanese Participant Cohort will be randomized as follows:

- Cohort 15 (n=5): a single IV dose active (n=4) or placebo (n=1).

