7. DISCONTINUATION OF STUDY INTERVENTION AND OF STUDY PARTICIPANT DISCONTINUATION/WITHDRAWAL

7.1. Discontinuation of Study Intervention

Note that discontinuation of study intervention does not represent withdrawal from the study. If study intervention is definitively discontinued, the participant will remain in the study to be evaluated for a minimum of 4 half-lives (approximately 70 days) after last dose. See the [SoA](#) for data to be collected at the time of discontinuation of study intervention and follow-up for any further evaluations that need to be completed.

In rare instances, it may be necessary for a participant to permanently discontinue study intervention (definitive discontinuation). Reasons for definitive discontinuation of study intervention include the following:

- Any participant who develops Grade 2 or higher adverse events for cardiac and blood/bone marrow categories and Grade 3 or higher adverse events in all other categories according to criteria defined in CTCAE, v. 5 will be discontinued from treatment, and followed until resolution of the adverse event(s).
- If a participant experiences symptoms typical of an allergic reaction, the study drug administration should be discontinued immediately and permanently;
- ECG changes (see below);
- Unacceptable toxicity;
- Pregnancy.

ECG Changes

A participant who meets the bulleted criteria based on the average of triplicate ECG readings will be withdrawn from the study intervention.

- QTcF >500 msec.

- Change from baseline: QTc >60 msec.

If a clinically significant finding is identified (including, but not limited to, changes from baseline in QTcF after enrollment), the investigator or qualified designee will determine if the participant can continue in the study and if any change in participant management is needed. This review of the ECG printed at the time of collection must be documented. Any new clinically relevant finding should be reported as an AE.

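### The two-thirds stopping rule in Part 1 does not exclude placebo recipients, so as written it cannot be met by active participants alone in Cohorts 1-3 and needs 6 of 6 active in the 6:2 cohorts

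*Protocol*

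**What the plan says.** Protocol Section 6.6.1 lists the criteria that terminate dose escalation in Part 1. The first concerns laboratory, ECG and vital-sign abnormalities and names its denominator: "If 50% or more of the participants receiving active drug at a given dose level (but not participants receiving placebo"). The second reads "If two-thirds of participants at a given dose level develop an individual participant stopping AE" and points to Section 7.1 for the event. It says nothing about active drug or placebo.

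Section 7.1 defines the individual stopping AE for everyone dosed: "Any participant who develops Grade 2 or higher adverse events for cardiac and blood/bone marrow categories and Grade 3 or higher adverse events" in the remaining categories.

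Section 4.1.1 gives the cohort splits:

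- Cohorts 1-3 are 2:2, for example "Cohort 1 (n=4): 0.3 mg active (n=2) or placebo (n=2), IV".
- Cohorts 4-8 and 10-14 are 6:2, for example "Cohort 4 (n=8): 10 mg active (n=6) or placebo (n=2), IV".
- The Japanese cohort is 4:1: "Cohort 15 (n=5): a single IV dose active (n=4) or placebo (n=1").

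Neither document states operating characteristics for the rule.

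**The concern.** The two bullets are adjacent and both count participants at a given dose level. If that phrase already left out placebo, the first bullet would not need its exclusion. The natural literal reading of the second bullet therefore counts the whole cohort. Placebo recipients are not expected to have drug-related stopping AEs, so including them dilutes the signal. Any placebo events that do occur count toward a stop, which has no safety logic.

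The gap is widest for non-serious symptomatic events. Section 7.1 covers them ("Grade 3 or higher adverse events in all other categories according to criteria defined in CTCAE, v. 5 will be discontinued from treatment"), but the 50% bullet does not, and the SAE pause applies only to serious events. For these events the two-thirds rule is the only criterion with a number attached.

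Section 6.6.1 also uses the stopping rules to decide whether the MTD has been reached, and Cohort 9 in Part 2 is dosed at the MTD or at the highest dose studied. A rule that fails to fire can therefore affect the Part 2 dose as well as the next Part 1 step.

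**Working it through.** **Inputs.** Threshold 2/3 (Section 6.6.1). Active:placebo splits 2:2, 6:2 and 4:1 (Section 4.1.1). As a check on the splits, the single-dose cohorts add to 3 × 4 + 5 × 8 = 52, with 3 × 2 + 5 × 6 = 36 active and 16 placebo, as in Section 9.2.1. The plan gives no figure for the rule itself to reproduce.

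**Events needed** = 2/3 × denominator, rounded up, for a fully dosed cohort.

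| Cohorts | All participants | Active only |
|---|---|---|
| 1-3 (2:2) | 2/3 × 4 = 2.67, so 3 | 2/3 × 2 = 1.33, so 2 of 2 |
| 4-8, 10-14 (6:2) | 2/3 × 8 = 5.33, so 6 | 2/3 × 6 = 4, so 4 of 6 |
| 15 (4:1) | 2/3 × 5 = 3.33, so 4 | 2/3 × 4 = 2.67, so 3 of 4 |

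With no placebo event and all participants counted:

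- 2:2 cohort: both active affected is 2/4 = 50%. The rule cannot fire.
- 6:2 cohort: 5 of 6 active affected is 5/8 = 62.5%, no stop. 6 of 6 is 6/8 = 75%, stop.

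Placebo events can make up the number: 2 active + 1 placebo or 1 + 2 stops a 2:2 cohort; 5 + 1 or 4 + 2 stops a 6:2 cohort.

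**Chance that the rule fires.** Stopping-AE rates are assumed, since the documents give none. Let A be the number of active participants affected, binomial with rate pa, and B the number of placebo participants affected, binomial with rate pp, independent of A.

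- 6:2: P(A + B ≥ 6) counting all; P(A ≥ 4) counting active only.
- 2:2: P(A + B ≥ 3) counting all; pa² counting active only.

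| Cohort and count | pa = 0.50 | 0.67 | 0.80 | 0.90 |
|---|---|---|---|---|
| 6:2, all, pp = 0 | 0.02 | 0.09 | 0.26 | 0.53 |
| 6:2, all, pp = 0.10 | 0.04 | 0.14 | 0.34 | 0.60 |
| 6:2, active only | 0.34 | 0.69 | 0.90 | 0.98 |
| 2:2, all, pp = 0 | 0 | 0 | 0 | 0 |
| 2:2, all, pp = 0.10 | 0.05 | 0.09 | 0.12 | 0.16 |
| 2:2, active only | 0.25 | 0.45 | 0.64 | 0.81 |

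For example, with pp = 0 and pa = 0.80, all six active must be affected: 0.80⁶ = 0.26.

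**The case against.** **The wording can be read the other way.** The exposure bullet in the same list also speaks of a dose level, and there it can only mean active recipients. Section 6.3.1 sets a dose level of the drug apart from placebo. The stated purpose of Section 6.6.1, finding the maximal tolerated dose, concerns active drug. This is fair, and an active-only reading is possible. It does not remove the problem: the neighbouring bullet's explicit exclusion, the any-participant scope of Section 7.1, and Section 4.1.1's use of dose level for a sentinel pair that includes a placebo recipient all point to the whole cohort. A mandatory stopping rule should not have two readings with such different triggers.

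**Other safeguards would act first.** These include the 50% rule, the SAE pause, sentinel dosing, sponsor-open review, an investigator stop that the sponsor team may not overrule, and the condition that "Progression to the next dose will occur if the last dose was well tolerated". They are real and make unsafe escalation unlikely. Apart from the 50% rule and the SAE pause, which do not reach non-serious symptomatic AEs, they rest on judgement. The table above gives the chance that one bullet fires, not the chance that escalation proceeds unsafely.

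**The most extreme result falls where the risk is lowest.** In Cohorts 1-3 the projected exposure margins are about 1,093-fold or more (Table 4). That stands; the 6:2 cohorts, which go up to 1000 mg, matter more.

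**False stops accumulate.** If every active participant in all three 2:2 and ten 6:2 cohorts had a 10% or 20% stopping-AE rate, the active-only rule would stop at least one cohort with probability of about 4% or 25%. The arithmetic is right, but a 20% rate of such events at every dose would itself call for review.

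**Conclusion.** The concern holds. As written, the rule does not end escalation when every active participant in a 2:2 cohort, or 5 of 6 in a 6:2 cohort, has a stopping AE and no placebo participant does. The counts follow from the text and do not depend on any assumed rate. They do assume that placebo is counted and that the cohort is fully dosed; Section 6.6.1 does not say how to apply the rule to a partly dosed cohort, where it could be met earlier. The probabilities rest on assumed rates and show scale only. Because the other safeguards remain, this should be corrected, but it does not by itself make the escalation scheme unsafe.

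**What to change.** Restrict the two-thirds bullet in Section 6.6.1 to active recipients, using the same qualifier as the bullet above. For example: *escalation ends when two-thirds or more of the active-drug recipients at a dose level, placebo recipients excluded, have a stopping AE as defined in Section 7.1*. Then state the counts: 2 of 2 in Cohorts 1-3, 4 of 6 in the eight-person cohorts, and 3 of 4 in Cohort 15 if the rule is meant to apply there (that cohort starts after single-dose escalation is complete).

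The cost is one clause and one line of counts, processed as a protocol amendment with IRB/EC approval. No new procedure is needed: the study is sponsor-open and the first bullet already requires counting active recipients. The chance of a false stop per cohort stays small. At an assumed active rate of 10% it is 0.001 in a 6:2 cohort and 0.01 in a 2:2 cohort; at 20% it is 0.017 and 0.04.
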